13. REFERENCES

14. APPENDICES

GLOSSARY OF ABBREVIATIONS

WC weight circumference

AWD abdominal wall depth

TRIAL SUMMARY

TRIAL TITLE

Investigating whether the abdominal waist circumference or abdominal girth can be employed as an accurate estimate of abdominal wall depth.

SHORT TITLE

Investigating whether the waist circumference can be used as an estimator of the depth of the abdomen as measured from the belly button.

DESIGN

Observational Study (Correlational Research)

AIMS

To assess the correlation between abdominal wall depth and waist circumference

To use this information in establishing a nomogram according to weight circumference for recommended Veres needle entry depth.

OUTCOME MEASURES

At the end of the study, it will be expected that the following will have been achieved

- 1. Production of correlation equation connecting waist circumference and abdominal wall depth
- 2. Description of weight relationship to abdominal adiposity.
- 3. Establishment of a safety nomogram guiding Veres needle insertion according to category of body waist circumference.

POPULATION ELIGIBILITY

Any mobile adult patient undergoing elective abdominal Computed Tomography Imaging (CT) or Magnetic Resonance Imaging (MRI) scans.

SAMPLE SIZE

385

[figure not shown]
DURATION

1 month

FUNDING AND SUPPORT IN KIND

(Names and contact details of ALL organisations providing funding and/or support in kind for this trial)	FINANCIAL AND NON FINANCIALSUPPORT GIVEN
EPSRC Digital Health and Care Centre for Doctoral Training (UKRI funded CDT)	PhD Studentship at the University of Bristol

TRIAL FLOW CHART

1. INTRODUCTION

1.1 BACKGROUND

Current abdominal entry during minimally invasive surgical techniques employs Veres needle insertion as one of the primary access mechanisms and by which a pneumoperitoneum within the peritoneal cavity is established. However, the procedure of needle insertion is of a blind nature with the result that entry associated injuries are unfortunately commonplace in laparoscopic abdominal surgery.

1.2 RATIONALE FOR CURRENT STUDY

This study seeks to assess whether the waist circumference can estimate the abdominal wall depth to a reliable degree of accuracy so as to be incorporated in a nomogram that would categorise suggested Veres needle abdominal insertion depth according to waist circumference range.

The research question is therefore 'Can the waist circumference be employed as an estimate of the abdominal wall depth?'

This would be helpful in guiding initial Veres entry into the abdominal cavity during laparoscopic (key-hole) or robotic surgery where entry is achieved blind without standardised depth advice. The traditional Body Mass Index (BMI) will also be taken to see if it makes a better correlation than abdominal girth. A study has previously been carried out analysing the relationship between BMI and vertical distance between umbilicus and retroperitoneal vessels (1) but we hypothesise waist circumference may be a better measure. The abdominal wall depth will be measured directly from abdominal Computed Tomography (CT) or Magnetic Resonance Imaging (MRI) scans with the waist, weight and height measurements to be physically taken from eligible consenting participants. The existence of a relationship that can be reliable in guiding needle depth investigation is hypothesised and requires further investigation.

Due to urgent need for safety mechanisms to be incorporated in the conduct of laparoscopic abdominal wall injury, this study attempts to provide some guidance into how deep the Veres needle should be inserted when a Veres needle is being used as the first entry abdominal device and insufflator. The study is aiming to improve safety in laparoscopic entry where a Veres needle is used by providing insertion depth guidance. It is aimed to reduce the number of failed entries or complicated entries.

2. STUDY OBJECTIVES

2.1 Primary Objectives

- 2.11. Investigate the correlation between waist circumference and abdominal wall depth through physical data collection. Waist circumferences will be obtained from patients as actual physical measurements and not estimated while the abdominal wall depth will be ascertained from each patient's corresponding cross sectional image.
- 2.12 Measure the abdominal wall depth of each participant from their cross sectional image. During laparoscopy, patients are in the same supine position and with patients required to be still during their scan, a reliable depth measurement can be taken as a proxy for their actual abdominal wall depth.

Produce descriptive statistics of the depths in the cohort of patients. Group each 1cm of abdominal wall depths by categories of waist circumference

2.13. Produce a nomogram for use as a predictor of abdominal wall depth.

2.2 Secondary Objectives

- 2.21. Assess the relationship of abdominal wall depth to BMI. Is BMI an inferior proxy measurement for abdominal wall depth?
- 2.22 How does the estimated (from CT scan) compare to actual wall depth (from actual Veres needle insertion depth in a future validation study-follow up of those patients who had surgery involving Veres needle pneumoperitoneum after their scan)

3. STUDY DESIGN

Quantitative Observational Study (Cross Sectional Study)

Participant physical measurements (waist circumference (cm), height(cm), weight(kg)) and the depth in centimetres of the associated abdominal wall depth taken from the corresponding radiological image.

These variables will be subjected to mathematical analysis in establishing correlations and building a nomogram.

A minimum of 385 participants and associated radiological scans of various weights(kg) will be recruited on a rolling basis. Recruitment will be at the time of patient presentation for their scan in the radiology department.

3.1 STUDY OUTCOME MEASURES

- 3.12 Production of correlation equation connecting waist circumference and abdominal wall depth
- 3.13 Description of weight relationship to abdominal adiposity.
- 3.14 Establishment of a safety nomogram guiding Veres needle insertion according to category of body waist circumference.

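### The equation and safety nomogram are unconditional deliverables: the accuracy condition in section 1.2 is never quantified, and no result counts as failure

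*Protocol*

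**What the plan says.** Section 1.2 poses a question open to either answer: "Can the waist circumference be employed as an estimate of the abdominal wall depth". It sets out to learn whether waist circumference "can estimate the abdominal wall depth to a reliable degree of accuracy so as to be incorporated in a nomogram", and it treats a dependable relationship as a hypothesis still to be tested.

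The sections that fix the objectives and outcomes are worded differently:

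- Objective 2.13: "Produce a nomogram for use as a predictor of abdominal wall depth".
- Section 3.1, item 3.12: "Production of correlation equation connecting waist circumference and abdominal wall depth".
- Section 3.1, item 3.13: "Description of weight relationship to abdominal adiposity".
- Section 3.1, item 3.14: "Establishment of a safety nomogram guiding Veres needle insertion according to category of body waist circumference".
- Trial Summary, outcome measures: the same three items, introduced by "At the end of the study, it will be expected that the following will have been achieved".

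Section 3 sends the measurements to correlation and to building the nomogram. Section 7 names correlational analysis in R and a sample size of 385. Objective 2.22 leaves comparison with actual needle depth to a later validation study.

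**The concern.** The rationale makes the nomogram conditional, and the objectives and outcomes do not. No section puts a value on the accuracy required, whether as an error in cm, a correlation or a coverage. An outcome measure should be a quantity whose value can come out well or badly. Here the outcomes are products, and each exists once the data have been collected and processed.

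This matters because the product is described as a safety tool for a needle insertion that section 1.1 itself calls blind. Investigators who follow 2.13 and 3.14 as written would issue a depth guide even if waist circumference told them little about an individual's wall depth. Because comparison with real needle depth is deferred, no other step in this study would expose an uninformative chart.

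**Working it through.** **1. Does the sample size imply an accuracy target?** Section 7 gives 95% confidence, a population of 56 million and 5% (labelled a standard deviation). The figure is reproduced by the formula for the precision of a single proportion, reading the 5% as the margin of error and assuming p = 0.5, which the protocol does not state:

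- n0 = z² p(1 − p)/e² = 1.960² × 0.25/0.05² = 384.15
- with finite-population correction, n0/(1 + (n0 − 1)/56,000,000) = 384.14, rounded up to 385.

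This concerns the precision of a percentage. Neither a correlation nor an error in predicted depth enters it, so the sample size supplies no implicit accuracy criterion.

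**2. Can the outcomes fail?** Set side by side, section 1.2 has a condition ("to a reliable degree of accuracy so as to be incorporated in a nomogram") without a value, while 2.13, 3.12, 3.14 and the Trial Summary have no condition. A regression line and a table of depths by waist category can be calculated from any 385 pairs with some spread in waist, including pairs with no association. This follows from the definitions and needs no simulation or assumed distribution.

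**3. Would a significance test serve as the missing condition?** The protocol does not propose one, but it is the natural default for a correlational analysis. Inputs: n = 385 (section 7), a two-sided 5% level (assumed), and Fisher's z with standard error 1/√(385 − 3) = 1/19.545.

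- Smallest significant |r| = tanh(1.960/19.545) = 0.100.
- Power at true r = 0.20: atanh(0.20) × 19.545 = 0.2027 × 19.545 = 3.96; 3.96 − 1.96 = 2.00; Φ(2.00) = 97.7%.
- Width of an individual prediction interval relative to ignoring waist, for a linear relation with constant residual spread: √(1 − r²).

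| True r | Power for r ≠ 0 | Relative width | Narrowing |
|---|---|---|---|
| 0.10 | 50% | 0.995 | 0.5% |
| 0.20 | 97.7% | 0.980 | 2.0% |
| 0.70 | about 100% | 0.714 | 28.6% |

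At this sample size, significance says almost nothing about whether waist circumference is useful for one patient. Even at r = 0.7 about 71% of the depth SD remains. Whether that is acceptable depends on the depth SD in cm, which the protocol does not give, and on the error that can be tolerated.

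**The case against.** The strongest reply is that the plan can deliver bad news. Objective 2.11 is to investigate the correlation, the first aim in the Trial Summary is to assess it, and the second builds the nomogram on that information. Objective 2.21 asks openly whether BMI is inferior. The summary's wording on achievement states an expectation and is not a rule that a nomogram must be issued.

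This reply stands against a stronger reading. A reader might infer that the study is certain to reach a positive conclusion, or cannot answer its own question in the negative. The documents do not support that. Producing an equation does not answer the question in section 1.2, and a near-zero correlation could be reported as such. With no decision rule, the probability of a positive conclusion is undefined; it is not 1.

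Three further points have some weight:

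- Objective 2.12 groups depths by waist category, so the spread within categories may be visible to readers. It does not say what spread would be too much.
- Nothing in the protocol puts the nomogram into clinical use; section 12 provides only for publication. That limits the immediate consequence, but a published chart described as a safety guide is meant to be used.
- The method of internal validation is detail that an analysis plan may supply. The conflict itself lies in the protocol: an accuracy threshold in an analysis plan would sit under a primary objective and an outcome that ignore it.

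**Conclusion.** The point holds in a limited form. The protocol's stated outcomes can be met whatever the data show, its one accuracy condition is neither quantified nor carried into the objectives and outcomes, and no result is defined as failure. An honest negative report remains possible but is left to judgement after the data are seen.

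That the deliverables can always be produced rests on no assumption. The figures against a bare significance criterion rest on n = 385, a two-sided 5% level, the Fisher approximation and a linear relation with constant residual spread. They are expressed relative to the depth SD because the protocol gives none. The change should be made before data are analysed; it does not affect recruitment or measurement.

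**What to change.** Reword objective 2.13, outcome 3.14 and the matching summary lines so that they can fail, for example:

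*A nomogram will be proposed only if the internally validated 95% limits of individual prediction error for wall depth from waist circumference (a) lie within a margin in cm set by the investigators before the data are seen, and (b) are narrower than the limits obtained by using the cohort-mean depth for everyone. Otherwise the study will conclude that waist circumference has not been shown to be accurate enough, and no nomogram will be issued.*

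Both parts are needed. Part (b) alone could be met by a very weak relationship. Part (a) alone could be met without any help from waist circumference if depths happen to vary little. A significant correlation should not be the criterion. The margin is for the investigators to choose and justify. The introductory line to the summary's outcome measures should also allow for the negative conclusion.

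The cost is protocol wording and one analysis step (bootstrap or cross-validation) on data already being collected, with no extra participants or measurements. The downside is that the study may end without a nomogram.

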8.3 CONFIDENTIALITY

The Chief Investigator will preserve the confidentiality of participants taking part in the study and will abide by the Data Protection Act. Each scan performed has a unique patient identifier and will be requisite to retrieve the scan images. However, this will be mapped to a pseudonymised code that won't immediately identify the patient's scan instance. To avoid 'losing' scan instances through incorrect patient identifiers, the patient's hospital number will additionally be noted. Each scan will be anonymised and once the abdominal wall depth has been measured and associated to the respective patient's physical measurement with the patient being identified through a code, we will no longer need the hospital number and will instead use the pseudonymised code. Data such as age, gender & ethnicity will also be collected and not shared to any party outside of the research group. This data will be stored in a password restricted university laptop and the measures in place to store data in a secure fashion will follow general data protection regulations. It will not be possible to identify individual participants from the data linked to the pseudonymised code and only the research personnel will have access to this data. Person identifiable data will not be required. The physical measurement data will be retained for 10 years and destroyed thereafter. It will be retained securely should it be required for future use.

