14.22 Metric measurements

Units of measurements (metric)				
Waist circumference	cm			
Weight	kg			
Height	cm			
Abdominal wall depth	cm			

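### The outcome list and second aim promise a safety nomogram and a recommended needle depth, but the data collected can support only a chart that predicts abdominal wall depth

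*Protocol*

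**What the plan says.** The protocol describes one chart in two ways.

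- **Stronger description.** Section 3.1, item 3.14, and the third outcome in the Trial Summary promise the "Establishment of a safety nomogram guiding Veres needle insertion" by category of waist circumference. The second aim in the Trial Summary wants a nomogram "for recommended Veres needle entry depth".
- **More modest description.** Objective 2.13 asks for a nomogram that predicts abdominal wall depth. Objective 2.12 groups measured depths by waist category as the descriptive step before it.

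The data are listed consistently. Section 3 names waist circumference, height and weight, and from the scan "the depth in centimetres of the associated abdominal wall depth taken from the corresponding radiological image". Section 14.22 lists the same four quantities. The schedule in section 14.4 has wall depth as its only image post-processing task. Section 8.3 adds that "Data such as age, gender & ethnicity will also be collected".

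Section 6 rules out follow-up, and objective 2.22 assigns the comparison with real needle depth to a future validation study. Section 1.2 mentions an earlier study "analysing the relationship between BMI and vertical distance between umbilicus and retroperitoneal vessels", but that distance is not a variable here. Item 3.13 promises a "Description of weight relationship to abdominal adiposity", with no definition of adiposity.

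**The concern.** Wall depth locates the inner edge of the abdominal wall. Calling a chart of it a safety tool, or reading a recommended entry depth from it, needs further information: how far structures lie behind the wall, or what happened when needles were inserted. The study plans to collect neither.

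The label matters because of the intended use. Sections 1.1 and 1.2 describe a blind procedure with known entry injuries and state the goal of fewer failed or complicated entries. If the study runs exactly as planned and is reported under the name in item 3.14, readers could take the chart as evidence on entry injury. The study would hold no such evidence.

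**Working it through.** The question is which variables exist, so the check matches each claim to the data it needs.

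**1. The protocol's one computed figure.** Section 7 gives a sample size of 385. It is reproduced by n = z² p(1−p)/e² with z = 1.96, p = 0.5 (assumed; not stated) and e = 0.05, reading the 5% as a margin of error: 1.96² × 0.25 / 0.05² = 384.16, rounded up to 385. It has no bearing on this point, because no sample size supplies a variable that is not measured.

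**2. Claims against data.**

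| Claim | Data needed | Planned? |
|---|---|---|
| Wall depth predicted from waist (2.13) | Waist and wall depth in the same people | Yes, both for every participant (sections 3, 14.22) |
| Spread of individual depths around the prediction | The same pair | Yes |
| Room behind the wall | Distance from wall to deeper structures | No (sections 3, 14.22, 14.4) |
| Failed or complicated entries | Observed needle entries | No (section 6: no follow-up) |
| Agreement of image depth with needle depth | Needle depth in the same people | No; deferred (2.22) |

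The first two rows support the chart in objective 2.13. The last three are what the safety and recommended-depth wording would need, and the count is 0 of 385 for each.

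**3. Why individual prediction limits belong on the chart.** Assume a straight-line fit with constant residual SD s. At the mean waist circumference, the standard error of the fitted mean is s√(1/385), and the standard error for predicting one new person is s√(1 + 1/385). Their ratio is √386 ≈ 19.6. A confidence band for the mean would therefore be about one twentieth as wide as the limits that apply to one patient. This ratio needs no assumed value of s. Such limits describe uncertainty about where the wall ends. They still say nothing about what lies beyond it.

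**4. Item 3.13.** Neither sections 3, 8.3 and 14.22 nor the objectives name a variable for abdominal adiposity. Objective 2.21, on BMI and wall depth, has no matching line in section 3.1. This is a gap in definition and does not carry the main point.

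**The case against.** The other side has real strength.

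- **The chart can be built.** A reader might infer that neither item 3.13 nor item 3.14 can be produced from the data. The documents do not support that. Waist and wall depth are planned for everyone, and section 3 says the variables are for building a nomogram. Only the safety and recommended-depth wording lacks support.
- **Adiposity is undefined, not unmeasurable.** Waist circumference or wall depth could serve as an indirect proxy if the protocol said so, and an analysis plan that is not shown might say so.
- **The vessel distance is a different quantity.** A reader might infer that the earlier study measured just what is missing here. As section 1.2 words it, that distance starts at the umbilicus, so it is not clearance beyond the wall. The section cites that work to compare BMI with waist as predictors, not as a design to copy.
- **No size of error can be claimed.** A reader might infer that prediction error is too wide for use. The protocol gives neither an SD of wall depth nor an expected correlation, so no figure in centimetres can be attached.
- **The authors hedge.** Section 1.2 treats a reliable relationship as a hypothesis needing more work and speaks of some guidance, and objective 2.22 foresees validation.

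All of this narrows the point. It does not remove it. The hedges are absent from the second aim and item 3.14, which state what the study will deliver. An analysis plan could define a proxy, but it could not supply an unmeasured distance or an unobserved entry.

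**Conclusion.** The point holds in this form: the second aim and item 3.14 go beyond objective 2.13 and beyond the data. The study can produce a chart of wall depth by waist circumference and quantify its error for individuals. It cannot conclude that needle entry guided by the chart is safe, nor recommend an entry depth.

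The size is categorical: no planned participant has a measured distance to deeper structures, an entry outcome or a needle depth. The conclusion assumes only that the variable lists in sections 3, 8.3, 14.22 and 14.4 are complete. It does not depend on an assumed SD or correlation.

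This should be corrected, because it changes what the study may claim on a safety matter. The undefined adiposity variable and the missing BMI outcome line are secondary.

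**What to change.** **Main change.** Reconcile the Trial Summary and section 3.1 with objective 2.13. Restate item 3.14, its copy in the Trial Summary and the second aim as a prediction chart for abdominal wall depth by waist circumference, with individual 95% prediction limits. Drop the safety and recommended-depth wording until the validation study foreseen in objective 2.22 has reported. This needs no new data; the cost is a more modest headline claim.

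**Optional.** Record the umbilicus-to-retroperitoneal-vessel distance on the same image as context. This costs one further measurement per scan and would not by itself validate a safety claim. Decide before the images are processed: section 8.3 stops using the hospital number once wall depth is linked, which may make later re-measurement harder.

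**Secondary.** In item 3.13, either name the variable that stands for abdominal adiposity or restate the item as the relationship of weight and BMI to wall depth. The second option also gives objective 2.21 a matching outcome. Either is a wording change.

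Nothing here proposes an insertion depth or a rule for needle entry.

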4. PARTICIPANT ENTRY

Participants undergoing routine abdominal or pelvic CT scans will have their waist circumference measured immediately prior to the scan commencing upon appropriate positioning. The weight and height are routinely collected physical measurements on arrival.

4.1 PRE-REGISTRATION EVALUATIONS

Participant body weight (kg), waist circumference (cm) and height (cm)

